4.1.1 Downloading regulatory documents

Download the site registration forms from the protocol-specific page located on the CTSU members' website. Permission to view and download this protocol and its supporting documents is restricted based on person and site roster assignment. To

participate, the institution and its associated investigators and staff must be associated with the LPO or a Participating Organization on the protocol.

- Log on to the CTSU members' website (<https://www.ctsuo.org>) using your CTEP-IAM username and password,
- Click on *Protocols* in the upper left of your screen
 - Enter the protocol number in the search field at the top of the protocol tree, or
 - Click on the By Lead Organization folder to expand, then select *AMC*, and protocol number *AMC-115*,
- Click on *Documents*, select *Site Registration*, and download and complete the forms provided. (Note: For sites under the CIRB initiative, IRB data will load automatically to the CTSU as described above.)

4.1.2 Protocol-specific requirements for site registration

Upon site registration approval in RSS, the enrolling site may access OPEN to complete enrollments. The enrolling site will select their credentialed provider enrolling the subject in the OPEN credentialing screen and will answer enrollment questions based on the eligibility checklist.

4.1.3 Submitting regulatory documents

Submit required forms and documents to the CTSU Regulatory Office via the Regulatory Submission Portal on the CTSU website.

To access the Regulatory Submission Portal, log on to the CTSU members' website → Regulatory → Regulatory Submission.

Institutions with participants waiting that are unable to use the Regulatory Submission Portal should alert the CTSU Regulatory Office immediately at [name] in order to receive further instruction and support.

Delegation of tasks log (DTL)

Each site must complete a protocol-specific registration packet, including an AMC DTL using the provided AMC template or local equivalent. The Clinical Investigator (CI) is required to review and sign the DTL prior to the site receiving an approved site registration status and enrolling participants to the study. The AMC DTL template is provided in the protocol registration packet for this protocol, located on the AMC Operations web site at www.AIDSCancer.org. Any individual at the enrolling site on a participating roster may initiate the site DTL. Instructions on completing the DTL are embedded in the AMC DTL template.

4.1.4 The AMC DTL must be updated contemporaneously as personnel are added or removed and/or study roles and delegated tasks change. Changes must be approved by the CI, and documented by his/her initials and date, before they are implemented.

4.1.5 Checking site registration status

You can verify your site's registration status on the members' side of the CTSU website.

- Log on to the CTSU members' website
- Click on *Regulatory* at the top of your screen
- Click on *Site Registration*
- Enter your 5-character CTEP Institution Code and click on Go

Note: The status shown only reflects institutional compliance with site registration requirements as outlined above. It does not reflect compliance with protocol requirements for individuals participating on the protocol or the enrolling investigator's status with the NCI or their affiliated networks.

4.3 Participant Registration

Sites must have this protocol approved by the NCI Central Institutional Review Board (CIRB) and be registered for study participation with the AMC Operations and Data Management Center (ODMC) before they may enroll participants.

After an informed consent form has been signed by the participant and it has been determined that the participant is eligible, the participant must be registered on-line via the Oncology Patient Enrollment Network (OPEN).

4.3.1 OPEN

The Oncology Patient Enrollment Network (OPEN) is a web-based registration system available on a 24/7 basis. OPEN is integrated with CTSU regulatory and roster data and with the Lead Protocol Organization (LPOs) registration/randomization systems for retrieval of participant registration assignments. OPEN will populate the patient enrollment data in NCI's clinical data management system, Medidata Rave.

Requirements for OPEN access:

- A valid CTEP-IAM account.
- To perform enrollments or request slot reservations: Be on the AMC roster, or Participating Organization roster with the role of Registrar. Registrars must hold a minimum of an AP registration type.
- If a DTL is required for the study, the registrar(s) must hold the OPEN Registrar task on the DTL for the site.
- Have an approved site registration for a protocol prior to patient enrollment.

To assign an Investigator (IVR) or Non-Physician Investigator (NPiVR) as the crediting, consenting, or receiving investigator for a patient transfer in OPEN, the IVR or NPiVR must list the IRB number used on the site's IRB approval on their Form FDA 1572 in RCR. If a DTL is required for the study, the IVR or NPiVR must be assigned the appropriate OPEN-related tasks on the DTL.

Prior to accessing OPEN, site staff should verify the following:

- Patient has met all eligibility criteria within the protocol stated timeframes, and
- All participants have signed an appropriate consent form and HIPAA authorization form (if applicable).

Note: The OPEN system will provide the site with a printable confirmation of registration information. Please print this confirmation for your records.

Access OPEN at **<https://open.ctsuo.org>** or from the OPEN link on the CTSU website **<https://www.ctsuo.org>**. Further instructional information is in the OPEN section of the AMC members' website at **www.AIDSCancer.org**. For any additional questions, contact the AMC ODMC (contact information in protocol roster).

4.3.3 OPEN questions

Further instructional information on OPEN is provided on the OPEN link of the CTSU website at <https://www.ctsuo.org> or at <https://open.ctsuo.org>. For any additional questions contact the CTSU Help Desk at [name] or [contact].

5.0 TREATMENT PLAN

This is a non-interventional study. Please refer to the Study Design ([Section 2.3](#)), Clinical and laboratory evaluations ([Section 8](#)), and Measurement of Effect ([Section 9](#)) for a description of the trial procedures.

5.1 Duration of Follow-Up

For participants not currently receiving cancer therapy, participation only involves the initial encounter for study data collection. For participants initiating therapy or currently under treatment, a short-interval follow-up will occur at 12 Weeks (\pm 2 Weeks). This is expected to coincide with planned treatments/clinical follow-up and therefore minimize unnecessary clinic visits that could increase participant burden (see [Section 8.3](#) for requirements).

6.0 ADVERSE EVENTS: LIST AND REPORTING REQUIREMENTS

As this study is non-interventional that focuses on data collection with limited follow-up, no adverse event data will be collected.

7.0 PHARMACEUTICAL INFORMATION

Not applicable (non-interventional study).

8.0 CLINICAL AND LABORATORY EVALUATIONS AND DATA COLLECTION

Evaluations required for this protocol are enumerated below and summarized in the Schedule of Events in [Appendix I](#).

8.1 Screening

All PWH who present for care at participating AMC clinical trial sites with a histologically confirmed diagnosis of cancer (within the past 5 years) will be tracked on a screening list. Eligibility will be assessed for each patient on the list, and if they are determined eligible, they will be approached to participate in AMC-115.

To determine the types of cancer cases that present to the clinical sites, all participants presenting at these sites have a minimum set of de-identified data collected. This minimal risk data collection will only include the participant's age, sex at birth, race/ethnicity, and type of cancer and will be performed prior to formal consent. Data collected during screening will be maintained separately from data on enrolled cases. This data will be compared to the total number of enrolled participants at each site to estimate the proportion of participants who consent to participate in this trial.

The protocol chair has established a set of IT logic codes that can be applied to electronic health record (EHR) systems to automate screening for "HIV status" among cancer patients. This is critical as it (1) makes the ascertainment of PWH and cancer uniform across participating domestic AMC sites and (2) reduces physician and study coordinator burden by leveraging the electronic medical record and automating the search. To ensure that this IT-based approach can be implemented across domestic AMC sites, the feasibility survey included a question specifically about the ability of sites to search their electronic medical record systems for HIV-specific disease codes.

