Laser Surgery	2	3	10	0	15
MSK	5	8	5	5	23
Montefiore	2	15	15	15	47
Moffitt	3	20	15	20	58
Boston Medical Center	8	8	15	15	46
Virginia Mason	7	3	4	4	18
Miami Cancer Institute	5	30	25	25	85
George Washington	2	5	10	10	27
Puerto Rico	2	4	4	2	12
UCSF	2	1	5	3	11
UCSD	32	59	23	52	166
UNC	4	4	2	4	14
Total	139	210	169	245	763

The above estimates indicate that sites, including those with a history of consistent enrollment onto AMC trials and new sites added in current AMC grant years, see 763 cancer cases with underlying HIV infection each year. Even with a conservative patient participation rate for this minimal burden study, the protocol chairs deem the target accrual range (360-720) to be feasible.

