12.0 ETHICAL AND REGULATORY CONSIDERATIONS

12.1 IRB Approval and Informed Consent

Records of all study review and approval documents must be kept on file by the Investigator and are subject to inspection during or after completion of the study. The IRB should receive notification of completion of the study and final report within 3 months of study completion and termination. The Investigator will maintain an accurate and complete record of all submissions made to the IRB, including a list of all reports and documents submitted.

To determine the types of cancer cases that present to the clinical sites, it is requested that all cancer patients presenting at these sites have a minimum set of de-identified data collected. This will be performed prior to formal consent and meets criteria for minimal risk data collection. Data collected on cancer patients presenting to the clinical site will include age, sex at birth, race/ethnicity, and type of cancer. Data collected during screening will be maintained separately from data on enrolled cases. No other data will be collected on patients who do not consent to participate in AMC-115.

Written informed consent will be obtained from the participant to collect identifiable data. The nature, significance and risks associated with the study must be explained to the participant. The informed consent will describe the purpose of the study, the procedures to be followed, the risks and benefits of participation, all risks of the investigational agent(s) and/or study participation as listed in the model informed consent form, and all other elements of informed consent as required by regulation. A copy of the consent form will be given to the participant to keep.

In addition, any institution(s) conducting research according to the guidelines of this protocol is required to adhere to local and national laws and regulations governing the confidentiality and disclosure of health information.

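### The consent proportion in Section 8.1 is an enrolled-to-screened fraction, and the permitted screening data cannot separate refusal from ineligibility or non-approach

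*Combined protocol and SAP*

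**What the plan says.** Section 8.1 describes a sequence. PWH who present for care "with a histologically confirmed diagnosis of cancer (within the past 5 years) will be tracked on a screening list". Then: "Eligibility will be assessed for each patient on the list, and if they are determined eligible, they will be approached to participate in AMC-115". A separate paragraph says that "all participants presenting at these sites have a minimum set of de-identified data collected", and that this collection "will only include the participant's age, sex at birth, race/ethnicity, and type of cancer and will be performed prior to formal consent". The screening data are kept apart from the data on enrolled cases, and are to be "compared to the total number of enrolled participants at each site to estimate the proportion of participants who consent to participate in this trial". No formula is given.

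Section 12.1 repeats the four descriptors and adds: "No other data will be collected on patients who do not consent to participate in AMC-115". It describes the screened group as cancer patients presenting at the sites, with no HIV restriction in that sentence.

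Section 3.1 sets eligibility: able to understand and willing to sign consent (3.1.1), HIV positive (3.1.2), diagnosed with or treated for cancer within 5 years (3.1.3), aged 18 or over (3.1.4), and presenting for clinical care or research (3.1.5). Section 3.2 adds no other exclusion.

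On expected volume, Section 10.2.2 says the 16 sites in Table 10-B "see 763 cancer cases with underlying HIV infection each year".

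**The concern.** A consent proportion should answer one question: of the eligible people who were asked, how many agreed? The comparison in Section 8.1 answers another: of everyone screened, how many ended up enrolled? The two agree only if every screened person is eligible and approached, and every enrolled person was screened.

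The analyst cannot repair this afterwards. Of the ways a listed person can fail to enroll, only being under 18 can be seen in the four permitted fields. Lack of capacity to consent, never being asked, and refusal all look the same.

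The study exists partly to learn about people who opt out of research (Sections 2.1 and 2.2). The figure is to be estimated by site, so a site that approaches fewer of its listed patients would appear to have less willing patients.

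**Working it through.** **Figures in the plan.** The documents state no consent rate, ineligible share or approach rate, so there is no figure for this quantity to reproduce. The neighbouring planning figures do reproduce: the Table 10-B site totals sum to 763 a year, 20 × 36 = 720, and 10 × 36 = 360.

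**Formula.** Let
- c = consent rate among those eligible and approached;
- f = share of listed people who are eligible and approached;
- s = share of enrolled participants who are not on the list.

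The Section 8.1 ratio is then R = c × f / (1 − s). It equals c only when f = 1 − s.

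**Effect of f alone (s = 0).** The relative shortfall is 1 − f. The documents give neither c nor f, so these values are assumed:

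| f | R if c = 50% | R if c = 80% |
|---|---|---|
| 0.99 | 49.5% | 79.2% |
| 0.95 | 47.5% | 76.0% |
| 0.90 | 45.0% | 72.0% |
| 0.80 | 40.0% | 64.0% |
| 0.50 | 25.0% | 40.0% |

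Two sites with the same 50% consent rate, one with f = 0.95 and one with f = 0.80, would show 47.5% and 40.0%.

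**Effect of s.** With c = 50% and f = 0.95:
- s = 0: R = 47.5%
- s = 5%: R = 0.475 / 0.95 = 50.0%
- s = 10%: R = 0.475 / 0.90 = 52.8%

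A modest number of enrollees missing from the list can cancel or reverse the shortfall.

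**Why s may exceed zero.** The populations differ:
- *Histology.* The list in 8.1 requires it; 3.1.3 does not. Section 8.2.7 records clinical and cytological diagnosis as possible methods, so enrollment without histology is foreseen.
- *Five-year window.* The list refers to diagnosis; 3.1.3 also admits treatment within 5 years.
- *Presentation.* The list refers to care; 3.1.5 also admits presentation for research.
- *HIV.* Section 8.1 limits the list to PWH; 12.1 states no such limit for the screened group. Read literally, 12.1 would enlarge the denominator by an amount that the documents do not let one calculate.

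**What the planning figures imply.** If all 16 sites list for 36 months at the Table 10-B rate, 3 × 763 = 2,289 would be listed. Then 720 / 2,289 = 31.5% and 360 / 2,289 = 15.7%. With s = 0, a ratio of 31.5% fits c = 31.5% with f = 1, c = 50% with f = 0.63 (0.315 / 0.50), or c = 80% with f = 0.39 (0.315 / 0.80). The permitted data could not tell these apart.

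**The case against.** The strongest reply is that f should be close to 1 by design. Section 8.1 has every listed patient assessed and every eligible one approached. Listing already requires HIV and recent cancer, so eligibility adds little beyond adult age and consent, and minors can be removed using the age field. This stands as far as size goes: a 1% to 10% loss moves a 50% rate only to 49.5% to 45%. It does not remove the problem, because the study collects nothing that would show whether f was in fact near 1.

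A reader might infer that the reported figure will fall far below true consent, and take 31.5% or 15.7% as evidence. The documents do not support that. Those percentages are target accrual over projected caseload and would be the same whether the gap came from refusal or from non-approach. They also assume 36 full months of listing at all 16 sites, whereas the synopsis gives about 3 years for accrual and follow-up together. Table 10-B counts annual cancers seen, so a person may be counted in more than one year. Nor do the documents say that listing continues once 720 are enrolled.

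Two further objections stand. The ratio feeds no primary or secondary endpoint (Sections 10.1 and 10.3), and it is not the only view of selection: the four descriptors can be compared between listed and enrolled people, and Section 10.1.2 compares cancer types with an external linkage study. Also, 3.1.1 makes willingness to sign an eligibility criterion, so a denominator of eligible patients taken literally would drop the refusers and drive the proportion towards 100%. The fix has to allow for this.

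**Conclusion.** The point holds as a problem of definition and of missing data. Under Sections 8.1 and 12.1, the figure labelled as a consent proportion is an enrolled-to-screened fraction. It mixes refusal with ineligibility and non-approach, its numerator is not fully contained in its denominator, and the permitted fields do not allow the parts to be separated.

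The size and direction of the distortion are unknown. If the plan is followed closely and few enrollees are missing from the list, the effect is small; the illustrations above rest on assumed values of c, f and s. A general claim that the figure will be too low goes beyond the documents, since off-list enrollees push it up. The consequence is limited to a descriptive by-site measure, but as planned that measure cannot be interpreted as consent.

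**What to change.** Amend Sections 8.1 and 12.1 as follows.

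1. Allow three de-identified yes/no fields per listed person: eligible, approached, consented. For this purpose define eligible as meeting 3.1.2 to 3.1.5 and having capacity to consent, leaving out willingness to sign.
2. Define the consent proportion as consented / (eligible and approached).
3. Report enrolled / listed separately as screening coverage, and the number eligible but not approached as a count by site.
4. Align the listed population in 8.1 and 12.1 with Section 3.1: PWH, with the same cancer and presentation criteria, so that every enrolled participant is on the list.

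The cost is a small expansion of de-identified pre-consent data beyond a limit that the protocol now states explicitly, and a short amendment. Section 12.2 requires CTEP and CIRB approval for it. Sites already assess eligibility and approach patients, so the fields record steps already taken. The change is best made early, because approaches and refusals not recorded at the time may not be recoverable.

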8.2 Enrollment Data Collection

Following informed consent, additional, identifiable data will be collected, including:

- 8.2.1 Patient characteristics: Date of birth, biological sex, gender identity, race, ethnicity, height and weight
- 8.2.2 Sociodemographic: Socioeconomic status (e.g., ZIP code, housing status [homeless y/n, categories for frequency of housing insecurity]), health insurance (insured/uninsured, type if insured)
- 8.2.3 Health behaviors: Tobacco use (type, exposure [pack/day, years use]), illicit drug use (ever, type, years exposure), alcohol use (ever, exposure [drinks/week], years exposure)
- 8.2.4 Comorbid conditions: Hepatitis B and C co-infection, cardiovascular disease (y/n, type), psychiatric conditions (y/n, type), non-cancer pulmonary conditions (y/n, type), hepatic dysfunction, hematologic abnormalities, renal dysfunction, neurologic disorders, endocrine disorders (including thyroid disorders, and diabetes)
- 8.2.5 HIV care: Current ART regimen, years of ART use, year of HIV diagnosis, history of opportunistic infections, most recent HIV viral load and CD4+T-cell count relative to participant visit).

8.2.6 Status of cancer diagnosis (one of the following):

- New diagnosis, pre-treatment phase
- New diagnosis, treatment phase
- Prior diagnosis, in remission (within 5 years of initial diagnosis or treatment)
- Prior diagnosis, recurrent, pre-treatment phase
- Prior diagnosis, recurrent, treatment phase
- Prior diagnosis, recurrent, no treatment planned

8.2.7 For participants with a new diagnosis (pre-treatment or treatment), the following will be collected:

- Cancer type, date of cancer diagnosis, method of diagnosis (clinical, cytology, histology), type of pathology performed (Hematoxylin and Eosin, immunohistochemistry, other), date of pathology, staging, staging methods (clinical, radiographic, surgical), date(s) of staging, current ECOG Performance Status (PS), current laboratory values (this would include complete blood count, renal and liver function, electrolytes)
- Cancer treatment plan: Detailed planned or current treatment. This should encompass surgical interventions, radiotherapy, and chemotherapy (agent names), including dates of planned or current therapy, and whether cancer care is being received or will occur at the enrolling institution.

8.2.8 For participants with a prior diagnosis in remission, the following will be collected:

- Cancer history: Cancer type, date of diagnosis, prior method of diagnosis (cytology, histology), pathology performed, date of pathology, staging, staging methods (clinical, radiographic, surgical), current ECOG PS. Records from a prior diagnosis/treatment should be requested, but if they are unavailable, participant report will be sufficient.
- Current method of post-treatment surveillance (clinical, laboratory, radiographic), and current schedule of follow-up with this center.
- Prior cancer treatment. This should encompass surgical interventions, radiotherapy, and chemotherapy. Records from a prior diagnosis/treatment should be requested, but if they are unavailable, participant report will be sufficient.

8.2.9 For participants with a prior diagnosis, recurrent (pre-treatment, treatment, or no planned treatment) the following will be collected:

- Initial cancer type, date of diagnosis
- Cancer history: prior method of diagnosis (cytology, histology), pathology performed, date of pathology, staging, staging methods (clinical, radiographic, surgical), date(s) of staging. Records from a prior diagnosis/treatment should be requested, but if they are unavailable, participant report will be sufficient.

- Prior cancer treatment. This should encompass surgical interventions, radiotherapy, and chemotherapy. Records from a prior diagnosis/treatment should be requested, but if they are unavailable, participant report will be sufficient.
- Current date of cancer diagnosis, method of diagnosis (clinical, cytology, histology), pathology performed, date of pathology, staging, staging methods (clinical, radiographic, surgical), date(s) of staging, current ECOG Performance Status (PS), current laboratory values (this would include complete blood count, renal and liver function, electrolytes).
- IF THERAPY IS PLANNED OR UNDERWAY: Detailed planned or current treatment. This should encompass surgical interventions, radiotherapy, and chemotherapy, dates of planned or current therapy, and whether cancer care is being received or will occur at the enrolling institution.
- IF NO THERAPY IS PLANNED: Reason for no further therapy, e.g., if the decision for no therapy is based on lack of options for treatment, lack of benefit of further treatment, or participant choice not to pursue further treatment.

8.2.10 Optional QoL questionnaires will be administered in the following languages understandable to the participant: English, Spanish, Italian, Chinese, Dutch, Amharic and Turkish. The QOL questionnaires have been validated for use in these languages and participants who do not speak English, Spanish, Italian, Chinese, Dutch, Amharic and Turkish will not be asked to complete these optional questionnaires. These questionnaires are optional for study participation:

- EORTC QLQ-C30: Global health status, physical functioning, role functioning, emotional functioning, cognitive functioning, social functioning, fatigue, nausea and vomiting, pain, dyspnea, insomnia, appetite loss, constipation, diarrhea, financial toxicity
- SCNS-SF34: psychological needs, health system and information needs, physical and daily living needs, patient care and support needs, sexuality needs

8.2.11 Biospecimens:

- As collection of HIV viral load or CD4 are standard of care for patients with HIV and cancer, HIV viral load and/or CD4 will be taken from the medical record from the date closest to the participant's visit. Biospecimens will not be collected as part of this study.

